The lashed epilation technique lacks a standardized method. Numerous studies conducted from 1967 to 2024 have demonstrated that approximately 40% of these studies utilize the Modified Coston method as outlined by Gao et al. in 2005. In this method, two lashes containing cylindrical dandruff (CD) were extracted from each eyelid of every participant using fine forceps. These lashes were then individually placed at opposite ends of a glass slide for observation under a slit-lamp biomicroscope (SL220; Carl Zeiss, Oberkochen, Germany) at a magnification of $\times 25$. This process resulted in eight lashes (4 per each eye) being prepared across four slides for each participant. A coverslip was applied to each lash, followed by the slow pipetting of 20 μL of saline at the coverslip's edge until it surrounded the lash. Subsequently, 20 μL of 100% alcohol (Sigma-Aldrich, St. Louis, MO) was pipetted at the same edge, extending the counting period for up to 20 minutes to facilitate the migration of embedded Demodex from the CD. The Demodex count was performed thrice under the microscope, and all samples were photographed using standard procedures by the same specialist. The presence of Demodex in at least one of the eight eyelashes was considered Demodex-positive.(22)

Regarding epilation techniques, there are three primary methods:

- A) Direct pulling,
- B) Rotating the lash before epilation, and
- C) Removing the cylindrical dandruff from the base of the lash before epilation.

Bitton et al. in 2024 concluded that Technique B, involving rotating the lash before epilation, yielded the highest Demodex count. (23)

In our study, we intend to use Technique B along with the Modified Coston method for counting Demodex mites. These distinct parameters and methodologies contribute to the understanding of demodex blepharitis treatment, but a comprehensive investigation of LLLT in this context is notably absent in the existing literature.

4.4) Eyelid scrubb compliance

Hyun Koo et al. (2012) demonstrated that good compliance with eyelid scrubbing using tea tree oil (TTO) (defined as more than 10 times per week with over 70% compliance) resulted in significant improvements in both Demodex count and the Ocular Surface Disease Index (OSDI) scores. In contrast, the moderate and poor compliance groups did not show statistically significant improvements compared to the control group.(6)

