2. Poor compliance with eyelid scrubbing using tea tree oil (TTO)
3. Dead demodex mite on lash.
4. Contraindication of IPL: Skin Fitzpatrick scale V/VI, patients with pigmented lesions on the treatment area (Eyelid, Cheek).
5. Pregnancy or breastfeeding.
6. Active Skin disease: facial skin cancer, graft-versus-host disease, systemic lupus erythaematosus
7. Active eye infection: recurrent herpes simplex
8. Other lid disease ocular trauma, ocular deformity scar, exophthalmos, eyelid insufficiency
9. Patients with pigmented lesion on area of treatment.

We will use computer-generated random number allocation into 4 groups in a 1:1:1:1 ratio including seed number, with the outcome assessor blind and participant blind with allocation concealment:

- 1.) ShamLLLT + ShamIPL
- 2.) LLLT + ShamIPL
- 3.) IPL + ShamLLLT
- 4.) LLLT + IPL

***All groups receive mechanical with pharmacological treatment (Warm compression + Lid hygiene + 1% TTO) for 90 days with google form logbook for record compliance and prevent co-interventional treatments.

***All group with participant/investigator/interpreter blind.

Blinding and Allocation Concealment in Research Team:

1st Research Assistant : Allocates patients according to computer-generated random number allocation, ensuring allocation concealment, Evaluated VA , IOP , OSDI score by reads the questionnaire to the participant

2nd Research Assistant (The treatment administrator) : Administers IPL, LLLT, or sham treatments.

3rd Research Assistant : Conducts assessments using Keratograph and Lipiview2.

Main Researcher : Evaluates primary and secondary outcomes using case record forms, remaining blind to the treatment groups.

Intervention Description

Mechanical with pharmacological treatment : Warm compression 15 minutes + Lid hygiene + 1% TTO for 90 days

1%TTO : OCuSOFT Oust Demodex Eyelid Cleanser Foam Bottle 50ml (OCuSOFT, Richmond, TX) is the only commercially available medication in Thailand that contains 1% tea tree oil.

IPL : The Eye-light device (Espansione Marketing S.p.A., Bologna, Italy, waveleggths 1,200-1,500 nm, Delivery system 12cm²) (Thai FDA No 66-2-2-0012685) :

- Protective eye shields
- 5 flashes of light were applied for each eye (3 along the inferior orbital rim, 1 at the lateral canthus, and 1 applied horizontally along the inferior orbital rim)
- Therapeutic energy level (10–16 joules/ cm²) based on the degree of skin pigmentation.

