2nd-5th visit	
 - 1st – 4th week : Treatment session 1 per week x 4 weeks - 8th week : 1 month after treatment (2nd Data correction+Epilation)
6th visit	- 16 th week : 3 months after treatment(3 rd Data correction+Epilation)

All data will be collected using Microsoft Excel version 16.65 (Microsoft Inc, USA) and analyzed using SPSS Statistics.

Informed consent process: The study includes an informed consent (Board consent) process that allows the use of research data for future studies without the need for additional consent. . Data will be collected after this process and recorded by the investigator in a manner that subjects cannot be identified

Log book:

Provide a paper logbook to all participants to record compliance and prevent any potential co-intervention by patients or caregivers.

11. Data Analysis and Statistics

Sampling technique and Sample size: N=22 in each arm by

1-Way ANOVA Pairwise, 2-Sided Equality

$$n = 2\left(\sigma \frac{z_{1-\frac{\alpha}{2\tau}} + z_{1-\beta}}{\mu_A - \mu_B}\right)^2$$

$$1 - \beta = \Phi(z - z_{1-\alpha/(2\tau)})_+ \Phi(-z - z_{1-\alpha/(2\tau)}), z = \frac{\mu_A - \mu_B}{\sigma \sqrt{\frac{2}{n}}}$$

$$n = 2 \left(3.56 \frac{z_{1-\frac{0.05}{2\tau}} + z_{1-\beta}}{3.18 - 1.59} \right)^2$$

$$1 - \beta = \Phi(z - z_{1-\alpha/(2\tau)})_+ \Phi(-z - z_{1-\alpha/(2\tau)}), z = \frac{3.18 - 1.59}{3.56 \sqrt{\frac{2}{n}}}$$

n = Sample size (per pair) = 36, Each arm = 18, 20% drop out = 21.6 = 22 per arm

Φ = the standard Normal distribution function

Φ^{-1} = the standard Normal quantile function

α = Type I error, Significance level = 5%

β = Type II error, Power (1 - β): 80%

τ = the number of comparisons to be made = 6

Relative difference (δ) = 50% (or 0.50) by our expert opinion of minimal clinical significant difference

From previous study(28)

Standard deviation (σ) = Assume an estimated value based on available data or literature (28) = 3.56

(SD Demodex count at baseline)

$\mu_A = 3.18$

$\mu_B = 1.59$

Statistical analysis, plan, and data management

Demographic and baseline clinical characteristics will be presented as percentages for categorical data and as mean with standard deviation or median with interquartile range (IQR) for continuous data.

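### The sample size rests on a baseline SD and an undated mean, neither justified as a week-8 value on background tea tree oil, so the 1.59-mite difference is probably optimistic

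*Combined protocol and SAP*

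**What the plan says.** Section 11 (sample size) uses a method titled "1-Way ANOVA Pairwise, 2-Sided Equality", with a 5% significance level, 80% power and "τ = the number of comparisons to be made = 6". The means are μA = 3.18 and μB = 1.59, and the SD is 3.56. The target is described as "Relative difference (δ) = 50% (or 0.50) by our expert opinion of minimal clinical significant difference", so μB is half of μA. The inputs are attributed to reference 28, which the reference list shows as an IPL study in meibomian gland dysfunction with and without Demodex. The SD carries the label "SD Demodex count at baseline". The mean carries no time point and is not assigned to a named arm.

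Section 10 sets the primary outcome as the right-eye Demodex count at week 8, 30 days after the light or sham sessions end. Section 9 says: "All groups receive mechanical with pharmacological treatment (Warm compression + Lid hygiene + 1% TTO) for 90 days". That includes the double-sham arm. Section 4.4 reports from an earlier TTO scrub study that good compliance "resulted in significant improvements in both Demodex count and the Ocular Surface Disease Index (OSDI) scores", whereas moderate and poor compliance showed no significant improvement. Section 11 gives no expected week-8 count on this background regimen and makes no allowance for a fall in the control arm.

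**The concern.** A sample-size calculation should use the mean and SD expected at the time of the primary comparison, under the treatment the comparator receives. Here the SD is a pre-treatment figure, and the mean comes from the same source with nothing to show that it is an on-treatment figure. The comparator at week 8 is on an active regimen that the plan's own literature section expects to reduce mites. The alternative hypothesis in Section 6 is superiority over that regimen, so its expected mean matters.

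The target is a relative halving, so the absolute difference shrinks with the control mean. If the background regimen works, the trial must detect fewer than 1.59 mites. A null result could then reflect an effective background treatment and be misread as failure of low-level light therapy or IPL.

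**Working it through.** **Inputs from Section 11.** μA = 3.18, μB = 1.59, σ = 3.56, two-sided α = 0.05, τ = 6, power 80%. The two normal quantiles are z(1 − 0.05/12) = 2.638 and z(0.80) = 0.842, which sum to 3.480.

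**The plan's own figure.** Its formula gives n = 2 × (3.56 × 3.480 / 1.59)² = 121.4, so 122 per arm. The plan states 36 per pair, 18 per arm, and 22 after 20% dropout (18 × 1.2 = 21.6). The stated figure does not follow from the stated inputs. That is a separate and larger problem; 122 is the reference value here.

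**Assumption for the control fall.** The documents give no week-8 count on TTO, so let the control mean fall by an assumed fraction r from 3.18, and keep the relative target of 50%. The difference is d = 3.18 × (1 − r) × 0.50 = 1.59 × (1 − r). That gives 1.59 at r = 0, 1.19 at r = 25% and 0.80 at r = 50%.

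**Required n per arm (τ = 6, 80% power, before dropout).** n = 121.4 × (SD / 3.56)² / (1 − r)².

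| How the SD behaves | r = 0 | r = 25% | r = 50% |
|---|---|---|---|
| Proportional to the mean | 122 | 122 | 122 |
| Follows the square root of the mean | 122 | 121.4 / 0.75 → 162 | 121.4 / 0.50 → 243 |
| Held at 3.56 | 122 | 121.4 / 0.5625 → 216 | 121.4 / 0.25 → 486 |

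**Power at 22 per arm, all evaluable.** Using the plan's power formula with z = d / (SD × √(2/22)):

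- r = 0: z = 1.59 / 1.073 = 1.481, and Φ(1.481 − 2.638) = 12.4%.
- SD held at 3.56: 6.3% at r = 25% and 2.9% at r = 50%.
- SD following the square root of the mean: 8.8% and 5.6%.
- SD proportional to the mean: 12.4% throughout.

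With 18 evaluable per arm and the SD held, the figures for r = 0, 25% and 50% are 9.7%, 5.1% and 2.5%.

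**The case against.** Four points can be made for the plan.

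- **The baseline label belongs to the SD only.** A reader might infer that Section 11 demonstrably uses the control arm's pre-treatment mean as its week-8 result. The documents do not say that. The time point of 3.18 is unstated, μA is not named as the control arm, and the six comparisons include active against active. The shared source makes a baseline reading reasonable, but it remains an inference. The active arms also receive TTO, so the question applies to every pair.
- **The difference is not proven to be too large.** This trial requires cylindrical dandruff and a live mite, samples lashes with collarettes and rotates them, which Section 4.3 says gave the highest count. Its starting count could exceed 3.18, so an on-TTO count near 3.18 cannot be excluded. Section 4.4 gives neither the size of the TTO effect nor the strength used in the cited study. These points stand and limit the claim to probably optimistic.
- **The compliance premise is unsettled.** Section 4.4 says moderate and poor compliers will be excluded; the exclusion list in Section 9 names only poor compliance. If moderate compliers stay, the expected control fall is smaller.
- **The cost in sample size depends on the model.** It is nil if the SD is proportional to the mean. A negative binomial model with baseline dispersion held gives about 71, 79 and 95 per arm for falls of 0, 25 and 50% if 3.18 is treated as a single count. If 3.18 is a per-lash mean and the four-lash total is modelled (mean 12.72, SD 14.24), it gives about 65, 67 and 71. A reader might also extend the fixed-SD row to a 75% fall and conclude that 1943 per arm are needed. That would imply a coefficient of variation of about 4.5 in controls (3.56 / 0.795) and 9.0 in the active arm, against 1.12 at the start (3.56 / 3.18). That is implausible for a count and should not be used as a requirement.

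**Conclusion.** The sizing inputs are not matched to the primary comparison. The SD is a baseline value, the mean appears to be one, and neither is justified for week 8 on the background regimen. Since the target is half of the control mean, 1.59 is probably optimistic. At assumed control falls of 25% and 50% the same relative target is 1.19 and 0.80 mites.

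The size of the effect cannot be fixed from the documents. Under the plan's formula, the required number per arm runs from no change at 122 up to 216 (25% fall) or 486 (50% fall), depending on how the SD moves. Power at 22 per arm is at best 12.4% on these inputs and could be as low as 6.3% or 2.9%. Most of the shortfall comes from the separate arithmetic error (18 stated against 122 computed); the mismatched inputs would remain after that error is corrected. It would be wrong to conclude that this point alone requires a particular larger trial.

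**What to change.** In Section 11:

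1. State the time point of 3.18 and its unit (per lash or per eye).
2. Replace μA and σ with expected week-8 values under the background TTO regimen, with a source. The cited TTO scrub study could be checked, but the documents do not show whether it reports a usable week-8 mean and SD. If no source exists, state the assumed range.
3. Express the target as a ratio of 0.50 against that control mean.
4. Restate power at 22 per arm for control falls of 0, 25 and 50% under stated SD assumptions, in the same revision that corrects the sample-size arithmetic.

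Sections 4.4 and 9 must also be reconciled on which compliance levels are excluded, because this affects the expected control-arm fall.

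The cost is a recalculation and restated assumptions, with no added patients. The downside is a less favourable stated power.

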Evaporative dry eye in dry eye disease (DED) is a long-term, multifactorial condition affecting the tears and the ocular surface, with a huge worldwide impact. It encompasses two main types: aqueous deficient and evaporative dry eye(15). In the USA, DED incurs an indirect annual cost of US \$73.12 billion, equating to US \$15,596 per person, due to diminished productivity(16). Treatment costs vary by DED severity, ranging from US \$300 to US \$1100 per person across different countries (17). The global DED market, valued at USD 5.22 billion in 2019, is anticipated to reach USD 6.54 billion by 2027, with an annual growth rate of 4.7%.

Beyond financial concerns, various studies highlight DED as a burdensome condition associated with depression, which is a hidden problem often overlooked.

Artificial intelligent technology has revolutionized the field of ophthalmology, particularly in the analysis of meibomian gland images. By incorporating AI-based meibography, we can improve the accuracy and consistency of assessments related to glandular health, a crucial factor in managing MGD associated with Demodex blepharitis. Yuan et al. (2021) have demonstrated a reliable AI-based methodology for normalizing and segmenting meibomian gland images, offering substantial advancements over conventional techniques(18)

Our study pioneers a Factorial Randomized Control Trial (RCT) investigating Low-Level Laser Therapy (LLLT) for the treatment of demodex blepharitis, comparing it with Intense Pulsed Light (IPL), IPL combined with LLLT, and mechanical with pharmacological approaches. The aim is to address the limitations of mechanical with pharmacological treatment for demodex blepharitis, particularly in terms of the efficacy of innovative laser treatments, improved compliance, and reduced disease burden, ultimately leading to better treatment outcomes and

used AI-based meibography to evaluate the meibography photos which taken from demodex blepharitis patient before and after treatment.

Novel questions

1.Will Low-Level Light Therapy (LLLT) and/or Intense Pulsed Light (IPL) therapy synergistically or antagonistically improve the mean reduction of Demodex mite count in patients with Demodex blepharitis?

2.Will Low-Level Light Therapy (LLLT) and/or Intense Pulsed Light (IPL) therapy synergistically or antagonistically improve the Meibomian Gland Dysfunction (MGD) stage in patients with Demodex blepharitis?

4. Literature Review

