LLLT : The blue MY MASK-E (Espansione Marketing S.p.A., Bologna, Italy) (Thai FDA No 66-2-2-0012685)

- No eye shields
- Applying a special mask for 15 minutes, once a week for 4 weeks

ShamLLT : the MY MASK-E (Espansione Marketing S.p.A., Bologna, Italy) – No eye shields, applying a power off special mask for 15 minutes , once a week for 4 weeks

ShamIPL : the Eye-light device (Espansione Marketing S.p.A., Bologna, Italy) - Protective eye shields, 5 time for each eye with flashes of light off.

Epilation Strategies

the Modified Coston method as outlined by Gao et al. in 2005. In this method, two lashes containing cylindrical dandruff (CD) then additional **rotated around itself** were extracted from each eyelid of every participant using fine forceps. These lashes were then individually placed at opposite ends of a glass slide for observation under a slit-lamp biomicroscope (SL220; Carl Zeiss, Oberkochen, Germany) at a magnification of $\times 25$. This process resulted in four lashes of right eye being prepared across two slides for each participant. A coverslip was applied to each lash, followed by the slow pipetting of 20 μL of saline at the coverslip's edge until it surrounded the lash. Subsequently, 20 μL of 100% alcohol was pipetted at the same edge, extending the counting period for up to 20 minutes to facilitate the migration of embedded Demodex from the CD. The Demodex count was performed thrice under the microscope, and all samples were photographed using standard procedures by the same specialist. The presence of Demodex in at least one of the eight eyelashes was considered Demodex-positive

10. Data Collection:

Primary Outcome:

Mean of Demodex Count - the number of Demodex mites per eyelash on a total of 4 collarettes lashes epilation (2 from upper eyelid ,2 from lower eyelid and identification by anatomical imaginary line of nasal and temporal limbus) per right eye in 30 days after end of treatment. (8th week)

Secondary Outcomes:

1.Mean of Demodex Count - per right eye in 90 days after end of treatment.(16th week)

2.MGD staging (Severity)

[figure not shown]
OSDI questionnaire used to evaluate ocular dry eye symptoms.

OCULAR SURFACE DISEASE INDEX®					
Please answer the following questions by checking the box that best represents your answer.					
Have you experienced any of the following during the last week:					

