For outcome ,Continuous data : Meibomian gland area ratio, Meibomian gland length and width,Meibomian gland diameter deformation index ,Meibomian gland tortuosity index, Meibomian gland signal index should be analyzed using ANOVA, while binary outcomes and ordinal data Meibomian gland dysfunction staging (severity) should be assessed using the chi-square test.

Any unavailable data will be treated as missing and will not be included in any calculations. The report will specify the percentage of missing data in each category. Statistical significance will be determined by a p-value < 0.05.

12.Ethical Consideration

The submission of the research proposal to the Institutional Review Board on Human Research at the Faculty of Medicine, Chulalongkorn University marks a pivotal step in ensuring the ethical oversight and approval of the prospective Randomized Control Trial (RCT)

Respect for Person:

Informed Consent: The principle of respect for persons underscores the importance of obtaining informed consent. Ensuring that participants have a clear understanding of the study's purpose, procedures, potential risks, and benefits is crucial.

Researchers employ transparent and comprehensive communication in the informed consent process, elucidating the randomization process, details of each intervention, and the freedom to withdraw at any point without repercussions.

Researchers will provide comprehensive information to ensure that volunteers understand the research well and make independent decisions regarding participation, without coercion or undue influence. If volunteers have legal representatives or proxies, they will be the ones reviewing the informed consent document and providing witness signatures. Researchers will seek permission from the hospital director at Chulalongkorn Hospital and will anonymize data using codes without disclosing patients' names, surnames, or hospital identification numbers.

Beneficence/Non-maleficence:

Risk-Benefit Assessment: Ethical research necessitates a careful evaluation of potential benefits against risks. Researchers must strive to maximize the positive outcomes of the study while minimizing any harm to participants.

Continuous monitoring of the interventions for unexpected risks and a commitment to modify or halt the trial if harms outweigh benefits are imperative to uphold the principles of beneficence and non-maleficence.

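### No analysis is named for the primary week-8 Demodex count; the interaction, its scale, the use of baseline and the multiplicity rule are left open

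*Combined protocol and SAP*

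**What the plan says.** - **Primary outcome.** Section 10 defines it as "Mean of Demodex Count - the number of Demodex mites per eyelash on a total of 4 collarettes lashes epilation", right eye, at week 8. The list of outcomes after section 12 repeats it.
- **Analysis.** In the statistical analysis text of section 11, the ANOVA list holds only AI meibography measures and ends "Meibomian gland signal index should be analyzed using ANOVA". Chi-square goes to binary outcomes and ordinal MGD staging. The Demodex count is in neither list, and no other section gives its analysis.
- **Sample size.** Section 11 sizes the trial by "1-Way ANOVA Pairwise, 2-Sided Equality", with "τ = the number of comparisons to be made = 6" and α divided by 2τ. The effect is stated as "Relative difference (δ) = 50% (or 0.50) by our expert opinion of minimal clinical significant difference", entered as 3.18 against 1.59. The SD of 3.56 is labelled "SD Demodex count at baseline".
- **Significance.** "Statistical significance will be determined by a p-value < 0.05", with no mention of adjustment.
- **Question and design.** The first novel question asks whether LLLT and/or IPL will "synergistically or antagonistically improve the mean reduction of Demodex mite count in patients with Demodex blepharitis". Section 8 declares a 2x2 factorial trial. The null hypothesis in section 6 concerns the reduction in count, not the count at week 8.
- **Baseline.** The visiting schedule includes an epilation at the first visit, before treatment.

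**The concern.** The plan specifies analyses for secondary imaging measures but not for the outcome on which the trial is sized. Four decisions therefore stay open until data are available: the model, whether the outcome is the week-8 count or the change from baseline, the scale on which synergy or antagonism is judged, and the error control over pairwise comparisons.

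The sizing method does not fill the gap. Six pairwise comparisons of four arms contain no interaction contrast. The contrast could be built from the four arm means, but nothing commits the investigators to it or to a scale. A one-way ANOVA of the week-8 count also has no place for the baseline count, which is collected anyway. The section on risks names selective reporting as a hazard, and an unspecified primary analysis leaves room for it.

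**Working it through.** **The plan's own figure.** The sizing formula with its own inputs gives n = 2 × [3.56 × (2.638 + 0.842)/1.59]² ≈ 122 per arm, against the stated 18. That is a separate problem and this point does not depend on it. I use 18 per arm below because it is the number the plan expects to evaluate.

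**1. Family-wise error.** Four arms of 18 give 4 × 18 − 4 = 68 residual df. The two-sided critical t is 1.995 at 0.05 and 2.718 at 0.05/6 = 0.00833. The chance that at least one of six pairwise tests rejects when all arms are equal is the upper tail of the studentized range (4 means, 68 df) beyond √2 × t:
- at 0.05, ungated: 0.200
- at 0.05/6: 0.041
- at 0.05, only after a significant omnibus F test: 0.05 for normal data (4.6–4.7% in simulated negative-binomial data)
- the same gate when three arms are equal and the fourth is far away: the gate always opens, leaving three tests among equal arms, 0.12

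**2. Scale of the interaction.** Let each treatment halve the count and the effects multiply: means 3.18, 1.59, 1.59, 0.795.
- Ratio of ratios: (0.795/1.59)/(1.59/3.18) = 1, so no interaction.
- Difference of differences: 3.18 − 1.59 − 1.59 + 0.795 = +0.795, which reads as antagonism.

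Both are true statements about the same means.

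**3. Precision of the interaction.** Assumption: 3.18 and 3.56 are the mean and SD of the analysed count. Section 11 does not say whether they are per lash or a total, so both readings are shown.
- Negative-binomial dispersion k = (SD² − mean)/mean². As a total: (3.56² − 3.18)/3.18² = 0.939. Per lash, using a four-lash total with mean 12.72 and SD 14.24: (14.24² − 12.72)/12.72² = 1.175.
- SE of the log ratio of ratios = √Σ[(1/μ + k)/18] over the four arms: 0.605 (total), 0.548 (per lash).
- The 95% CI extends by a factor exp(1.96 × SE) either way: 3.27 (total), 2.93 (per lash).
- All arms receive lid hygiene and tea tree oil for 90 days, so the week-8 control mean may be below a baseline value. With a control mean of 1.59 (assumption, total reading, same k), SE = 0.723 and the factor is 4.1.
- On the raw scale with SD 3.56 in every arm, the interaction SE is 2 × 3.56/√18 = 1.68 mites. The 95% CI is ±3.29, wider than the assumed mean of 3.18.

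**4. Baseline.** The documents give no correlation between baseline and week 8. With baseline as a linear covariate the residual variance is multiplied by 1 − ρ²: 0.91, 0.75 or 0.51 for assumed ρ of 0.3, 0.5 or 0.7.

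**The case against.** Several points on the other side have force.

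- **The words on continuous data and ANOVA could be stretched to cover the count, and they do not say one-way.** A two-way factorial ANOVA is not excluded, and an analysis of change would use baseline. This stands: the criticisms about interaction and baseline apply if the sizing method is carried over to the week-8 count. It does not close the gap, because no section commits to either alternative.
- **The p<0.05 sentence is compatible with adjusted p-values, and the null hypothesis is an omnibus one.** A reader might infer that the trial will run at 20% family-wise error. The documents do not support that: 20% holds only for unadjusted, ungated tests, and an F gate would bring the global-null figure to about 5%. The gate still leaves up to about 12% when three arms are equal, and the plan does not mention one.
- **The documents lean towards absolute differences.** The novel question, the null hypothesis and the sizing formula are worded that way; only the clinical threshold is relative. This stands, and it means that a log-scale model departs from that wording.
- **A reader might infer that raw-scale ANOVA would falsely report antagonism.** In simulated halving trials it signals antagonism about 9% of the time. That is power for a real additive interaction of +0.80, not a false-positive rate to set against 2.5%.

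**Conclusion.** The plan must be changed before the data are analysed. It names no analysis for its primary outcome and plans no LLLT×IPL contrast, although its first question asks for one in a declared factorial design. It speaks of reduction in section 6 but of a week-8 count in section 10. It sizes at 0.05/6 but judges at p<0.05 without stating an adjustment. Family-wise error under the global null is about 20%, 5% or 4%, depending on which reading is adopted.

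The text-based findings need no numerical assumption. The interaction precision (a factor of about 3 either way with a control mean of 3.18, about 4 with 1.59) rests on reading the planning mean and SD as those of the analysed count and on 18 evaluable per arm. On any of these readings the trial can estimate the interaction but is unlikely to settle it.

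The documents do not support going further and saying that one particular model is required. Negative-binomial regression and factorial ANCOVA are both defensible; what is needed is a commitment to one.

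**What to change.** 1. **Name the primary analysis.** State one factorial model of the week-8 count with LLLT, IPL, LLLT×IPL and the baseline count as terms. Negative-binomial regression with a log link and number of lashes as offset suits a count whose planning SD exceeds its mean and keeps the per-lash definition; factorial ANCOVA is another choice. Align sections 6 and 10 on whether the outcome is the week-8 count or the reduction.
2. **Fix the interaction scale in advance.** If the log scale is chosen, say that it departs from the absolute-difference wording of the novel question, the hypothesis and the sizing formula. Report LLLT×IPL with a 95% CI as estimation only.
3. **State one multiplicity rule for the primary outcome** in place of the bare p<0.05, consistent with the six comparisons in the sizing, for example Holm or Bonferroni at family-wise 0.05.
4. **Do not read a non-significant LLLT versus IPL contrast as support** for the section 6 hypothesis that the two are equally effective.

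Cost: wording only, with no new data or visits, but a stricter threshold lowers pairwise power. In the halving scenario under the negative-binomial model, without baseline adjustment, moving from 0.05 to 0.05/6 (Bonferroni, or Holm's strictest step) takes power from 42–45% to 19–21% for control versus a single treatment and from 89–94% to 70–82% for control versus the combination (total to per-lash reading). With a control mean of 1.59 (total reading), the figures at 0.05/6 are 13% and 49%. Baseline adjustment may recover some of this loss; how much depends on a correlation that the documents do not give.
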